Title Page

Protocol Title: Validation of a risk matrix for severe postdischarge pain after ambulatory gynaecological laparoscopy

Protocol Version: 1

Brief Title: Predicting pain after ambulatory gynaecological laparoscopies

A study to investigate the validity of a pain prediction tool, developed for patients with gynaecological laparoscopic surgeries.

Institution responsible for the trial: Oslo University Hospital

Legal Registered Address: [name]

Approval Date:

Sponsor Signatory: [name]

[name]

Dec 19, 2025

Name

Date

Sponsor functions including Medical Monitors, Coordinating Investigator, and Principal Investigator Names and Contact Information can be found in Appendix 10

The Protocol Amendment Summary of Changes Table

Date	Protocol version	Section # and Name	Description of Change	Brief Rationale
291025	1.5	8.6.3. Recruitment Strategy	Written study information will be distributed digitally to patients scheduled for ambulatory surgery, together with their surgical appointment letter.	To ensure that patients have the opportunity to review the study details prior to surgery and make an informed decision regarding participation.
291025	1.5	8.6.5. Data Quality Assurance	Signed consent and Nettskjema registrations will be stored for 5 years after end of study (e.g. 31.12.30).	Not necessary to store data for more than 5 years according to REK.
291025	1.5	1. Protocol summary (1.1.-1.2.), 4. Study Design, 7. Study Assessments and Procedures.	Added assessing postoperative pain in the PACU.	Same as in previous study.
291025	1.5	8.3.1. General Considerations	Introduction of Clonidine intraoperatively for pain prophylaxis changes n needed to be included in the study.	May affect pain perception postoperatively.
291025	1.5	8.3.2.2. Main Analytical Approach	Including the variable “Treated with Clonidine, Yes/No”	Inclusion of patients receiving Clonidine intraoperatively.

291025	1.5	8.3.2.3. Sensitivity Analysis	Evaluation of original prediction model.	Changes in inclusion criteria due to changes in clinical practise.
291025	1.5	8.5. Sample size Determination	Increase in sample size from 165 to 207.	Change in number of variables in the logistic regression model.
291025	1.5	2.2. Background	Definition of the four risk factors for severe postdischarge pain.	Specifying which risk factors to be studied.

Table of Contents

Title Page	1
The Protocol Amendment Summary of Changes Table.....	2
Table of Contents	3

1.1. Synopsis

Protocol Title: Validation of a risk matrix for severe postdischarge pain after ambulatory gynaecological laparoscopy

Brief Title: Predicting pain after ambulatory gynaecological laparoscopies

Rationale:

Objectives, Endpoints, Assessments:

Objectives	Endpoints	Assessments
Primary		

 To validate a prediction tool for severe postdischarge pain (NRS 7-10) after gynaecological laparoscopic surgeries 	
 Worst pain since discharge from hospital within 24 h after surgery 	
 Pain assessment using the Verbal Numeric Rating Scale 0-10, on POD1

Study design: Prospective observational cohort study

This study design includes no masking.

Brief Summary:

The purpose of this study is to test and validate a newly developed risk matrix in a new sample of patients. The risk matrix will be a useful tool to preoperatively predict who is at risk for experiencing severe postoperative pain after discharge from ambulatory gynaecological surgery. When validated, the prediction tool will be implemented in everyday clinical practice with ambulatory gynaecological patients.

Study details include:

- The study duration will be up to 6-7 months.
- Data will be collected at three occasions, on the day of surgery, during PACU stay and on POD1.

Number of Participants:

Approximately 207 participants (minimum) will be enrolled in the study.

Schema

Procedure	Day of surgery	PACU	POD1	Notes
Written informed consent	x			
Inclusion/exclusion criteria	x			
Demography/Baseline data	x			Questionnaire
Postoperative pain		x		
Postdischarge pain			x	Postdischarge pain data collected by telephone follow-up
Intraoperative data collection			x	Patients' medical records (Dips and MetaVision)

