2.2. Background

Despite the gynaecological laparoscopic procedure being considered less invasive compared to laparotomy (Brown 2019), 20-40% of patients report severe pain postoperatively (Gerbershagen 2013, Cruz 2021), which can negatively impact quality of life, recovery, patient satisfaction, and healthcare resource utilisation. Most of these women undergo ambulatory surgery, meaning they arrive for the operation and return home the same day. Since they have limited access to stronger pain medication upon returning home and lack direct access to medical expertise, unlike inpatients, severe postoperative pain can be both uncomfortable and problematic.

In our previous study, we found that over 42% of the patients experienced severe postdischarge pain within the first 24 h after surgery, that is a pain score of 7-10 on the NRS. We identified 4 preoperative risk factors independently associated with severe postdischarge pain: younger age, presence of preoperative pain, pain expectation and preoperative use of opioids. Our findings may contribute to clinicians’ awareness of clinically relevant risk factors for severe postoperative pain in this patient population. Moreover, knowledge

on females-specific validated predictive factors for pain is important for successful treatment in gynaecological laparoscopic surgery which is one of the most common ambulatory surgical procedures (Joo, 2019).

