8.6.3. Recruitment Strategy

Written information on the study will be distributed digitally to patients scheduled for ambulatory surgery, together with their surgical appointment letter. This ensures that patients have the opportunity to review the study details prior to surgery and be prepared to make an informed decision regarding participation. On the day of surgery, patient recruitment will take place and written informed consent will be obtained by a member of the research team after the patient has confirmed their willingness to participate.

For patients scheduled on short notice, who may not have received the digital information letter in advance, the study information will be provided upon arrival by administrative staff or a nurse not affiliated with the research team. After the patient has read the information, the research team may approach the patient to discuss participation.

Data Protection

- Participants will be assigned a unique identifier in consecutive order. Any participant records or datasets that are transferred to the sponsor will contain the identifier only; participant names or any information which would make the participant identifiable will not be transferred.
- The participant must be informed that their personal study-related data will be used by the sponsor in accordance with local data protection law. The level of disclosure must also be explained to the participant who will be required to give consent for their data to be used as described in the informed consent
- Data will be recorded in Nettskjema and stored in Tjenester for Sensitive Data (TSD) (UiO).

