8.6.5. Data Quality Assurance

On the day of surgery, patients self-reported data will be directly recorded in Nettskjema, using a mobile phone or an Ipad. On POD1, a member of the research team or a research nurse will record data in Nettskjema during the follow-up call. In case paper solutions of the questionnaires are used, all data manually recorded will be double-checked by a member of the research team or a research nurse.

The sponsor or designee is responsible for the data management of this study, including quality checking of the data.

Signed consent and Nettskjema registrations will be stored for 5 years after end of study (e.g. 311232) or as long as recommended by REK.

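### The plan does not ensure that the person who elicits and enters the POD1 pain score is unaware of the patient's baseline predictors

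*Combined protocol and SAP*

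**What the plan says.** The synopsis (1.1) describes a prospective observational cohort and adds "This study design includes no masking". The endpoint is worst pain since discharge, assessed as "Pain assessment using the Verbal Numeric Rating Scale 0-10, on POD1", and the schema in the protocol summary shows that it is collected by telephone. Section 8.3.2.1 cuts it at 0–6 versus 7–10, and section 8.3.3 confirms that no other outcome is analysed.

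On who does what:

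- **Recruitment (8.6.3):** "On the day of surgery, patient recruitment will take place and written informed consent will be obtained by a member of the research team".
- **Baseline data (8.6.5):** by default, "patients self-reported data will be directly recorded in Nettskjema, using a mobile phone or an Ipad".
- **Paper forms (8.6.5):** only if paper is used, "all data manually recorded will be double-checked by a member of the research team or a research nurse".
- **Outcome (8.6.5):** "On POD1, a member of the research team or a research nurse will record data in Nettskjema during the follow-up call".

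The predictors to be validated are given in section 2.2 as "younger age, presence of preoperative pain, pain expectation and preoperative use of opioids".

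**The concern.** In a validation study the outcome should be obtained without knowledge of the predictors. Otherwise the outcome can drift towards what the tool predicts. Here a person on the telephone turns a spoken answer into a number, and one step on that scale, from 6 to 7, turns a non-event into an event. A caller who knows that a woman uses opioids and expects a lot of pain might probe further, or settle an answer such as 'six or seven' upwards, and do the reverse for a low-risk woman.

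Errors of that kind follow the predictors, so they make discrimination and the confusion matrix look better than they are. A larger sample does not remove them, and none of the analyses in section 8.3.2 would reveal them. The synopsis says that the tool will go into everyday practice once validated, so optimism in these measures matters.

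**Working it through.** **1. Is there a safeguard anywhere?** Reading sections 1.1, 4, 6.2, 7, 8.3 and 8.6 together:

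| Question | What the plan states |
|---|---|
| Must the caller differ from the recruiter? | Not addressed; both tasks can fall to a research team member (8.6.3, 8.6.5) |
| Is the caller barred from seeing T1 answers? | Not addressed |
| Is the question scripted? | Not addressed |
| Do staff see the predictors? | By default the patient enters them herself; staff check them only on paper forms (8.6.5) |
| When is the risk score computed? | Not stated outright. The matrix is applied to the collected data (8.3.1), and analysis follows completion of inclusion, with no interim look (Interim Analysis) |

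So the caller's independence from the predictors is neither ensured nor described. The plan does not say that it is breached.

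**2. The plan's own figures.** The plan needs 75 events for 5 variables, which is 75 / 5 = 15 events per variable. Then 75 / 0.40 = 187.5, rounded up to 188, and 188 × 1.10 = 206.8, rounded up to 207. These figures reproduce and are not affected by this point. They serve only as a base below.

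**3. Size, as illustration only.** The documents give no distribution of scores, no AUC and no rate of unclear answers, so every input here is assumed. Pain is taken as latent normal with 40% at NRS 7 or more, which puts about 17% at 6 and 15% at 7. The 40% of women with the highest predicted risk are called high risk. In a share *f* of calls, a 6 in a high-risk woman is recorded as 7, and a 7 in any other woman as 6. With 400,000 simulated patients:

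| *f* | Outcomes reclassified | Of 188 | AUC gain, true 0.65 | true 0.70 | true 0.75 |
|---|---|---|---|---|---|
| 5% | 0.74–0.76% | about 1.4 | 0.0072 | 0.0069 | 0.0066 |
| 10% | 1.45–1.55% | 2.7–2.9 | 0.0146 | 0.0134 | 0.0128 |
| 20% | 2.87–3.02% | 5.4–5.7 | 0.0291 | 0.0275 | 0.0251 |

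A hand count gives the same order. Assume 10% unclear answers: 188 × 0.10 = 18.8. Assume a quarter are settled in line with known risk: 18.8 × 0.25 = 4.7. If neutral handling would have settled half of those the same way, 4.7 × 0.5 = 2.35 outcomes actually move, and 2.35 / 188 = 1.25%.

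**4. Compared with sampling error.** With 75 events, 113 non-events and an assumed AUC of 0.70, the Hanley–McNeil formula uses Q1 = 0.70 / 1.30 = 0.538 and Q2 = 2 × 0.49 / 1.70 = 0.576. The variance is [0.21 + 74 × (0.538 − 0.49) + 112 × (0.576 − 0.49)] / (75 × 113), about 0.0016. The standard error is about 0.04 and the 95% half-width about 0.08. The illustrated bias is smaller than that, but it runs in one direction and the confidence interval does not reflect it.

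**The case against.** A reader might infer that the people who recruit each patient also call her, so that outcome assessment is not independent of the predictors. The documents do not say so. They describe a shared pool, the caller may be a research nurse, and no passage has the same individual do both tasks. Nor does obtaining consent in itself reveal pain expectation or opioid use, which are questionnaire items. The paper check is conditional, and its timing relative to the call is not given.

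A reader might also take the masking sentence as ruling out any masking of callers. It stands beside the design label and reads most naturally as a statement about a study with no allocated treatment. It does not say that callers see baseline data.

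The mechanism is limited too. The patient gives the number, and a fixed rule dichotomises it afterwards. Bias requires an unclear answer, a caller who knows the risk profile, and settlement in the expected direction, and the documents show none of these happening. The patient's knowledge of her own predictors cannot be masked at all. Sections 8.3.1 and Interim Analysis already imply that scores are computed after data collection.

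All of this stands, and it keeps the point narrow. It does not close the gap. The predictors are four simple items, and section 2.1 says that scoring takes under a minute, so a caller who knows the answers could judge risk without a computed score. Section 8 promises a more detailed analysis plan, but nothing supplied shows that it covers the conduct of the call.

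**Conclusion.** The point holds in limited form. The plan does not ensure that the POD1 caller is unaware of the baseline predictors, and it has no scripted question, for the only endpoint that is analysed. Any resulting bias would tend to favour the tool's AUC and confusion matrix. Its effect on the calibration slope is not clearly favourable, since the target there is 1 and a higher slope is not automatically better.

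The size cannot be estimated from the documents. Under the assumptions shown, the AUC gain is about 0.007 to 0.029, and it exceeds that only if shifting of borderline scores is more common than assumed. The stronger conclusion, that validation would be undermined, is not supported. This is an inexpensive improvement in conduct and reporting, not a flaw that invalidates the design.

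**What to change.** In sections 1.1 and 8.6.5, state that:

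- the POD1 caller has no access to that patient's T1 answers or to any risk score;
- the caller reads a fixed script that asks for one whole number from 0 to 10;
- where the existing rota allows, the caller did not recruit that patient or check her paper form;
- the identity code of the person making each call is recorded;
- the risk-matrix score is computed only after the POD1 outcome has been entered, as sections 8.3.1 and Interim Analysis already suggest.

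Where separation is not possible, report it as a limitation. The PACU pain score need not be withheld for this purpose, since it is not one of the four predictors.

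The cost is protocol wording, a short script, form-access settings in Nettskjema and some rota planning. The documents do not state staffing and report no funding, so separation of tasks is worded as conditional. Section 8.6.1 requires approval before changes to the study design are implemented, so a short amendment may be needed. Data collection is scheduled into spring 2026, and the change would protect calls made after it takes effect.

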1.3. Schedule of Activities (SoA)

2025

Activity	July	August	September	October	November	December	Spring 2026	Autumn 2026
Study applications OUS	x							

PVO/REK/Clinical Trials.com	x	x	x	x				
Data collection					x	x	x	
Analysis/writing article manuscript							x	
Publication								x

2. Introduction

Based on data from our previous study, “Preoperative factors associated with severe postdischarge pain after ambulatory gynaecological laparoscopy: a prospective cohort study”, we have developed a risk matrix to predict who will suffer from severe pain after surgery. The risk matrix needs to be validated in a new gynaecological patient sample and may become a useful tool for clinicians.

2.1. Study Rationale

As day surgery is increasingly preferred over in-hospital treatment due to feasibility and reduced economic costs, it is important to evaluate patient related outcomes such as comfort and safety after discharge. Most previous studies on predictors for postoperative pain have not been focused on postdischarge pain.

Early identification of patients at high risk for severe pain can contribute to better and more targeted individual pain prevention and management, thereby reducing the incidence of unnecessary pain and discomfort after surgery. By identifying and treating patients who are particularly vulnerable to severe postoperative pain, we can also reduce hospital stays, prevent unplanned admissions due to pain, decrease the number of outpatient inquiries related to pain, and expedite recovery and return to normal activities. This will contribute to reduced resource use, improved patient care, and hopefully increased patient satisfaction.

The risk matrix for severe postoperative pain has the potential to improve clinical practice by providing clinicians with a simple, evidence-based tool that can identify high-risk patients before surgery. The scoring takes less than one minute. Today, we do not have such instrument at hand. The results from this project could influence current routines and treatments at OUS and may also be applicable to other patient populations and other hospitals.

2.2. Background

Despite the gynaecological laparoscopic procedure being considered less invasive compared to laparotomy (Brown 2019), 20-40% of patients report severe pain postoperatively (Gerbershagen 2013, Cruz 2021), which can negatively impact quality of life, recovery, patient satisfaction, and healthcare resource utilisation. Most of these women undergo ambulatory surgery, meaning they arrive for the operation and return home the same day. Since they have limited access to stronger pain medication upon returning home and lack direct access to medical expertise, unlike inpatients, severe postoperative pain can be both uncomfortable and problematic.

In our previous study, we found that over 42% of the patients experienced severe postdischarge pain within the first 24 h after surgery, that is a pain score of 7-10 on the NRS. We identified 4 preoperative risk factors independently associated with severe postdischarge pain: younger age, presence of preoperative pain, pain expectation and preoperative use of opioids. Our findings may contribute to clinicians’ awareness of clinically relevant risk factors for severe postoperative pain in this patient population. Moreover, knowledge

on females-specific validated predictive factors for pain is important for successful treatment in gynaecological laparoscopic surgery which is one of the most common ambulatory surgical procedures (Joo, 2019).

2.3. Benefit/Risk Assessment

There is no risk connected to participation in the study. All patients will receive standard medical and surgical treatment throughout the study.

3. Objectives, Endpoints, and Estimands

Objectives	Endpoints	Assessments
Primary		
To validate a prediction tool for severe postdischarge pain (NRS 7-10) after gynaecological laparoscopic surgeries	Worst pain since discharge from hospital within 24 h after surgery	Pain assessment using the Verbal Numeric Rating Scale 0-10, on POD1

The primary clinical question of interest is to validate if the risk matrix developed previously using a different data set (i.e., a new population with similar patient and surgical characteristics) can predict severe pain after ambulatory gynaecological laparoscopy.

4. Study Design

Prospective observational cohort study

In this study, we will collect data necessary to validate a previously developed risk matrix, at two different time points: T1) preoperatively on the day of surgery, T2) during a follow-up call on POD1, to collect postdischarge pain data. In addition, patients' postoperative pain will be assessed using the NRS, during PACU stay.

Data to be collected:

- T1: Age, height, weight, living arrangement, education, employment status, financial concerns, smoking status, previous abdominal surgery, dysmenorrhea severity, preoperative pain, preoperative non-opioid analgesics/opioids, postoperative pain-expectation, preoperative anxiety related to surgery, insomnia, previous treatment for anxiety, depression or other psychological disorder.
- T2: Postdischarge pain on POD1: at rest, during activity, average pain, and worst pain since discharge. Non-opioid and opioids consumption after discharge will also be recorded. Any case of unplanned admission or health care contact.
- PACU: worst pain during PACU stay.
- Patients' medical records (Perioperative data): ASA classification, type of surgery, surgery duration, anaesthesia duration, intra- and postoperative medication.

Data will be registered in Nettskjema/TSD.

End-of-Study Definition

The end of the study is defined as having a complete data set for at least 207 patients.

A participant is considered to have completed the study if she has completed all questions including the follow-up call on POD1.

5. Study Population

Women scheduled for ambulatory gynaecological laparoscopy in general anaesthesia.

5.1. Inclusion Criteria

Participants are eligible to be included in the study only if all of the following criteria apply:

Age

1. Participant must be 18 years of age at the time of signing the informed consent.

Type of Participant and Disease Characteristics

Participants who are scheduled for ambulatory gynaecological laparoscopy, e.g. ovarian cyst removal, excision of endometriosis, salpingo-oophorectomy, salpingectomy, chromoperturbation, ovarian drilling for polycystic ovary syndrome, adhesion removal, diagnostic laparoscopy, oophorectomy, removal of migrated intrauterine device, sterilisation/tubal ligation.

Informed Consent

2. Capable of giving written informed consent.

Other Inclusion Criteria

3. Must speak and read Norwegian.

5.2. Exclusion Criteria

Participants are excluded from the study if any of the following criteria apply:

Medical Conditions

1. Severe psychiatric disorder, severe cognitive dysfunction.

Prior/Concomitant Therapy

2. Intraoperative ketamine or lidocaine infusion or regional anaesthesia.

Other Exclusion Criteria

3. Does not speak or read Norwegian.

5.3. Screen Failures

Examples of screen failure patients would be no time to fill out the questionnaire due to time constraints, loss to follow-up, loss of data recordings.

6. Discontinuation of Study Intervention and Participant Discontinuation/Withdrawal

Participant Discontinuation/Withdrawal from the Study

A participant may withdraw from the study at any time at the participant's own request for any reason (or without providing any reason).

- The right to request data deletion does not apply if the information is de-identified, included in analyses, or published.

